The main safety evaluation index	
(1) Common Terminology Criteria for Adverse Events (CTCAE) Grade 3 toxicity ratio
 
Evaluation time: 3 months \pm 7 days after the end of the last treatment.
 
Indicator definition: Proportion of subjects with grade 3 toxicity during the trial cycle.
 
Evaluation methodology: Investigators recorded AEs that occurred during the clinical trial cycle and graded them according to CTCAE V5.0.
 
(2) CTCAE grade 4 and 5 toxicity ratio
 
Evaluation time: the entire clinical trial cycle.
 
Indicator definition: Proportion of subjects with toxicity of grade 4 and 5 during the trial cycle.
 
Evaluation methodology: Investigators recorded AEs that occurred during the clinical trial cycle and graded them according to CTCAE V5.0.

Secondary effectiveness Evaluation indicators	
(1) Objective Response Rate (ORR) (three days, 1 month \pm 7 days, 2 months, \pm 7 days, 3 months, \pm 7 days after the end of the last treatment).
 
(2) DCR (three days, 1 month \pm 7 days, 2 months \pm 7 days) after the end of the last treatment
 
(3) Tumor markers (if required) (three days, 1 month \pm 7 days, 2 months \pm 7 days, 3 months \pm 7 days after the end of the last treatment).
 
(4) Tumor-specific symptoms (screening period, 1 month \pm 7 days, 2 months \pm 7 days, 3 months \pm 7 days).
 
(5) Product usability evaluation (ProBeam360 system, radiotherapy management software (Aria), radiotherapy planning software (Eclipse)) (the day of completion of the last treatment).

Secondary	
(1) CTCAE grade 1 and 2 toxicity ratio (3 months \pm 7 days after the end of the last

safety	treatment).
Evaluation indicators	
(2) Laboratory tests [3 days after the end of the last treatment, 1 Months \pm7 days, 2 months \pm7 days, 3 months \pm7 days].(3) Eastern Cooperative Oncology Group (ECOG) physical status grading [3 days after the end of the last treatment, 1 month\pm 7 days, 2 months\pm7 days, 3 months\pm7 days].(4) Incidence of adverse events (AEs) (3 months \pm 7 days after the end of the last treatment).(5) The incidence of Serious Adverse Events (SAEs) (3 months \pm 7 days after the end of the last treatment).(6) Incidence of device defects (after last treatment)

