DCR was calculated and the Clopper-Pearson method was used to calculate the 95% confidence interval for tumor disease control. ORR was calculated and the Clopper-Pearson method was used to calculate the objective response rate 95% confidence interval. Descriptive statistics on the percentage change from baseline of the measurable sum of the longest diameter (SLD). The Waterfall Chart was made by the maximum percentage reduction in SLD per participant compared to the screening period.

The *Kaplan-Meier* method was used to calculate the median duration of response, median progression-free survival, median survival, and overall survival, and plotted *K-M* curves (long-term follow-up data).

Safety analysis

[figure not shown]
Descriptive statistics were used to classify organ systems in MedDRA medical terms, and the incidence, occurrence, and severity of adverse events, adverse reactions, and serious adverse events were summarized.

Laboratory indicators, ECOG physical status grading and other safety-related indicators were compared and evaluated before and after treatment, and clinical evaluation [no clinical significance, clinically significant (tends to normal), clinically significant (tends to be abnormal), not checked], CTCAE grade evaluation before and after treatment cross-tab.

The central effect is considered in the analysis process, and the general linear model is used for the measurement data and CMH for the counting data.

The baseline data analysis was performed using the Full Analysis Set (FAS); Effectiveness analysis uses FAS and Per Protocol Set (PPS); Security analysis uses the Safety Set (SS).

Trial flowchart

The body of the protocol

1 Sponsor information

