2.1 Objective

Clinical trial (screening-short-term follow-up): The data obtained by using Proton Beam equipment (ProBeam360) for radiation therapy in tumor patients compared with the target value to evaluate the effectiveness and safety of ProBeam360 for radiation therapy in tumor patients to provide clinical basis for product registration application.

Long-term follow-up: The long-term efficacy and safety of ProBeam360 for radiation therapy in cancer patients were evaluated by using the long-term follow-up data of ProBeam360 for radiation therapy in cancer patients.

2.2 content

This clinical trial is a prospective study, carried out in 1 clinical trial institutions, and 47 patients with tumors of intracranial, head and neck, chest, abdomen, spine, pelvis, limbs and other tumors were selected as study subjects, all using investigational medical devices, and designed for a single group of target values. The research device involved in this trial is the proton therapy device (ProBeam360), a medical device for investigation. Short-term follow-up is: 1 visit during the screening period (within 4 weeks before the first treatment), 2~9 visits during the treatment period according to the length of treatment weeks (1~8 weeks), and 3 after the last treatment 3 visits within a month; Long-term follow-up was 11 visits over a period of 3~5 months after the end of the last treatment. The main efficacy evaluation index was DCR 3 months after the end of the last treatment, and the main safety evaluation index was the proportion of CTCAE grade 3 toxicity in the entire short-term follow-up clinical trial cycle and CTCAE grade 4 & 5 toxicity reactions in the entire short-term follow-up clinical trial cycle. The collected data were analyzed and compared with the target values, and the effectiveness and safety of ProBeam360 in proton radiation therapy for patients with tumors such as intracranial, head and neck, chest, abdomen, spine, pelvis, and extremities were evaluated.

3 Overall design

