Evaluation time: 3 months \pm 7 days after the last treatment.

Evaluation methodology: Investigators recorded AEs that occurred during the clinical trial cycle and graded them according to CTCAE V5.0.

Formula: Proportion of CTCAE grade 4 and 5 toxicities = (number of subjects with CTCAE grade 4 and 5 reactions in the test cycle) / total number of subjects × 100%

Judging criteria: See CTCAE V5.0 for details.

3.1.5.2 Secondary safety evaluation indicators and their methods and time selection for evaluation, recording and analysis

(1) CTCAE grade 1 and 2 toxicity ratio

Reason for selection: The proportion of CTCAE grade 3~5 toxicity reactions 3 months after the end of the last treatment was the main safety evaluation index, and the proportion of CTCAE grade 1 and grade 2 toxicity reactions was used as a secondary safety evaluation index for auxiliary evaluation.

Indicator definition: Proportion of subjects with grade 1 and 2 toxicity during the trial cycle.

Metric type: Qualitative.

Data collection time: the entire clinical trial cycle.

Evaluation time: 3 months ± 7 days after the last treatment.

Evaluation methodology: Investigators recorded AEs that occurred during the clinical trial cycle and graded them according to CTCAE V5.0.

Calculation formula: proportion of CTCAE grade 1 and 2 toxicities = (number of subjects with CTCAE grade 1 and 2 toxicities in the test cycle) / Total number of participants × 100%.

Judging criteria: See CTCAE V5.0 for details.

(2) Laboratory tests

Reason for selection: According to the Guidelines for Technical Review of Clinical Evaluation of Proton Carbon Ion Therapy System (CFDA Circular No. 4 of 2018), changes in clinical symptoms and signs should be recorded for clinical manifestations, tumor improvement (imaging examinations, laboratory test data), etc., and comprehensive analysis should be carried out. At the same time, it is a routine safety monitoring index for medical device clinical trials.

Data collection and evaluation time: screening period, treatment period 1st day per week (Monday to Sunday is regarded as 1 calendar week, each natural week on the day of the first treatment), before treatment or -1 day (blood count only), 3 days after the end of the last treatment, 1 month \pm 7 days (except coagulation routine), 2 months \pm 7 days (except coagulation routine), 3 months, \pm 7 days (except coagulation routine). .

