4.7.1 Data statistical methods

Statistical analysis with SAS 9.4 software.

All data are described statistically, including demographics, baselines, all efficacy measures, and all safety data. The measurement data give the mean, standard deviation, minimum, maximum, median, 25th quantile and 75th quantile; The counting data gives the frequency and the corresponding percentage.

Effectiveness Analysis:

The number and percentage of cases achieving DCR were calculated, and the Clopper-Pearson method was used to calculate the 95% confidence interval for tumor disease control rate. ORR was calculated and the Clopper-Pearson method was used to calculate the objective response rate 95% confidence interval. Descriptive statistics on the percentage change from baseline of the sum of the longest diameter (SLD) of the measurable tumor. The Waterfall Chart was made by the maximum percentage reduction in SLD per patient compared to the screening period.

The *Kaplan-Meier* method was used to calculate the median duration of response, median progression-free survival, median survival, and overall survival, and plotted *K-M* curves (long-term follow-up data).

For tumor markers, compare and evaluate the changes before and after treatment, and give clinical evaluation [no clinical significance, clinically significant (tend to normal), clinically significant (tend to be abnormal), not checked].

Safety Analysis:

Descriptive statistics were used to classify organ systems in MedDRA medical terms, and the incidence, occurrence, and severity of adverse events, adverse reactions, and serious adverse events were summarized.

Laboratory indicators, ECOG physical status classification and other safety-related indicators were compared and evaluated before and after treatment, and clinical evaluation ([no clinical significance, clinically significant (tending to normal), clinically significant (tending to abnormal), not checked], CTCAE grade evaluation before and after treatment cross-table.

4.7.2 Missing, unused, or erroneous data (including mid-exit and evacuation) and unreasonable data

All missing, unused or erroneous data (including mid-exit and withdrawal) and unreasonable data will be discussed and finalized by investigators and

biostatisticians during the blinding review phase. The basic statistical principles of these data processing are as follows:

- (1) Describe the details of each shedding case;
- (2) Missing data from baseline, which can not be estimated;

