5.5.2 Laboratory tests

The results of laboratory indicators (blood routine, coagulation routine, urine routine, blood biochemistry) and their changes from baseline were summarized and described at each planned visit, the changes before and after treatment were evaluated, and the pre- and post-treatment cross-over tables of clinical evaluation (normal, abnormal and clinically significant) were given.

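### The only planned categorical laboratory comparison is before versus after treatment, so a blood-count abnormality that appears and recovers during the course shows as unchanged in that table; a worst-grade table would count it (minor)

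*Protocol*

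**What the plan says.** **The comparison.** The protocol summary (Safety analysis) compares laboratory indicators before and after treatment and plans a "CTCAE grade evaluation before and after treatment cross-tab". Protocol 4.7.1 repeats this as a "CTCAE grade evaluation before and after treatment cross-table". SAP 5.5.2 summarises results and changes from baseline at each planned visit, and then states that "the pre- and post-treatment cross-over tables of clinical evaluation (normal, abnormal and clinically significant) were given". The SAP has no laboratory table by CTCAE grade.

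**The timing.** In the protocol summary, secondary safety indicator (2) begins "Laboratory tests [3 days after the end of the last treatment, 1 Months" and continues to 2 and 3 months, with no on-treatment time. Protocol 3.1.5.2 (2) has "Data collection and evaluation time: screening period, treatment period 1st day per week", with the weekly sample drawn "before treatment or -1 day (blood count only"), followed by the same four post-treatment times.

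**Baseline and unscheduled data.** SAP 4.1 takes the last non-missing value before first treatment as baseline. It summarises only scheduled laboratory results by visit, and unscheduled results are tabulated separately.

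**The concern.** Weekly counts taken during a course are neither before nor after it, so on the natural reading they do not enter the cross-table. Blood counts are the one laboratory test that the protocol repeats during treatment. The before/after table can therefore miss a fall in counts that has recovered by the follow-up visits.

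What is at stake is the completeness of a secondary, descriptive safety display. As planned, no laboratory table says how many subjects ever reached a given grade. There is then no tabulated check that on-treatment laboratory toxicity was also recorded as adverse events.

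**Working it through.** The plan states no figure to reproduce here, so the check sets the texts side by side and then counts scheduled samples.

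**1. Which planned outputs use a weekly on-treatment count?**

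| Output | Source | Uses weekly counts? | Counts subjects by worst grade? |
|---|---|---|---|
| CTCAE-grade cross-table | Protocol summary, 4.7.1 | No (before/after) | No |
| Clinical-category cross-table | SAP 5.5.2 | No (pre/post) | No |
| Values and change from baseline by visit | SAP 5.5.2 | Yes, as planned visits | No |
| CTCAE toxicity by grade | Protocol 3.1.5.1, SAP 5.5.1 | Only if recorded as an AE | Subjects at each grade, from AEs |

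Neither document specifies a worst post-baseline laboratory table.

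**2. What the cross-table does with a recovered count.** Take a subject with baseline grade b, a higher grade g in some treatment week, and grade b again at the post-treatment visits. The before/after table puts this subject in cell (b, b), meaning unchanged. A baseline-by-worst table puts the subject in cell (b, g).

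**3. How many scheduled counts fall outside the table.** Inputs:
- Course length w is 1 to 8 weeks (Protocol 2.2: "2~9 visits during the treatment period according to the length of treatment weeks (1~8 weeks").
- One count is taken per treatment week, before that day's treatment (3.1.5.2).
- Four counts follow treatment: 3 days and 1, 2 and 3 months (3.1.5.2).

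The week-1 count precedes the first fraction, so it belongs to baseline. That leaves w − 1 on-treatment counts and 4 post-treatment counts:

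share outside the table = (w − 1) / (w − 1 + 4)

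- w = 1: 0/4 = 0%
- w = 4: 3/7 = 43%
- w = 8: 7/11 = 64%

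Protocol 3.1.5.2 defines weeks as Monday to Sunday, so a course that starts midweek can touch one more calendar week. The share is then w / (w + 4): 1/5 = 20%, 4/8 = 50% and 8/12 = 67%.

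**4. Which tests are affected.** The weekly sample is a blood count only. Coagulation, urine, liver and kidney tests are not scheduled during treatment, so the table omits no planned on-treatment result for them.

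**The case against.** The strongest reply is that other planned outputs already show these data, and much of it stands.

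- **Per-visit summaries.** Weekly counts are planned evaluations, and SAP 5.5.2 summarises change from baseline at each planned visit. SAP 5.2 includes minimum, maximum and quartiles, so the lowest value at each week is visible. This stands. But a per-visit distribution does not count subjects who ever reached a grade: lowest values fall in different weeks, and the denominator shrinks as shorter courses end.
- **Adverse events.** A reader might infer that the before/after table hides on-treatment toxicity from the grade 3 and grade 4–5 pass/fail criteria. The documents do not support that. Protocol 3.1.5.1 and 4.5 define those criteria from AEs recorded and graded over the whole trial cycle, and SAP 5.5.1 counts subjects at each grade. A recovered event recorded as an AE still counts. What remains is that a laboratory value reaches this route only if the investigator records it as an AE, and I found no rule in either document for when that happens.
- **Wording.** Neither text names the after visit, and in SAP 5.5.2 the phrase follows the by-visit summary, so a series of by-visit cross-tables is a possible reading. Even then, no table gives each subject's worst grade.
- **Synopsis list.** It also omits screening, which a before/after comparison needs, so it may simply be an abbreviated list of follow-up times. That is plausible. It calls for aligning the text and does not show an intention to drop the weekly data.
- **Imputation.** SAP 4.4 carries the worst observation forward for missing safety values. It acts only when a value is missing, so it does nothing for a subject who attends and has recovered.

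**Conclusion.** The point holds as a minor one. The only planned categorical laboratory comparison omits the on-treatment blood counts, and a transient abnormality appears there as unchanged. Between 0% (1-week course) and 64% (8-week course) of scheduled counts after the first fraction fall outside the table, or 20% to 67% if the course touches one extra calendar week. These figures assume one count per treatment week and four after treatment. They count blood draws and do not estimate affected subjects or bias; the documents give no rate of on-treatment count abnormalities from which to estimate those.

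It would be too much to say that the laboratory analysis as a whole reports such toxicity as no change, or that a primary safety decision depends on this table. By-visit summaries show the values, and the primary criteria rest on AEs.

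Two inconsistencies belong with the point. The synopsis laboratory times differ from 3.1.5.2, and the SAP cross-table uses clinical categories where the protocol also specifies CTCAE grade.

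**What to change.** - In the protocol summary, Protocol 4.7.1 and SAP 5.5.2, define the laboratory cross-table as baseline CTCAE grade (the SAP 4.1 baseline) against each subject's worst grade from the first fraction to the month-3 visit, including weekly and unscheduled counts. State this as an exception to the SAP 4.1 rule that only scheduled results are summarised.
- Keep the before/after table as a second display, since it shows recovery.
- Use CTCAE grade in the SAP table, as the protocol states.
- Align the laboratory times in the synopsis with 3.1.5.2.
- Use the worst-grade table as a check that laboratory toxicity was recorded as AEs.

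The cost is wording in both documents and one more table, with no new tests or visits. The laboratory display will look less favourable, because recovered abnormalities will be counted.

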1.1 Name of the sponsor

Varian Medical Systems Trading (Beijing) Co., Ltd

1.3 The name, address, contact information and relevant qualification documents of the agent

NA

2 Purpose and content of clinical trial

2.1 Objective

Clinical trial (screening-short-term follow-up): The data obtained by using Proton Beam equipment (ProBeam360) for radiation therapy in tumor patients compared with the target value to evaluate the effectiveness and safety of ProBeam360 for radiation therapy in tumor patients to provide clinical basis for product registration application.

Long-term follow-up: The long-term efficacy and safety of ProBeam360 for radiation therapy in cancer patients were evaluated by using the long-term follow-up data of ProBeam360 for radiation therapy in cancer patients.

2.2 content

This clinical trial is a prospective study, carried out in 1 clinical trial institutions, and 47 patients with tumors of intracranial, head and neck, chest, abdomen, spine, pelvis, limbs and other tumors were selected as study subjects, all using investigational medical devices, and designed for a single group of target values. The research device involved in this trial is the proton therapy device (ProBeam360), a medical device for investigation. Short-term follow-up is: 1 visit during the screening period (within 4 weeks before the first treatment), 2~9 visits during the treatment period according to the length of treatment weeks (1~8 weeks), and 3 after the last treatment 3 visits within a month; Long-term follow-up was 11 visits over a period of 3~5 months after the end of the last treatment. The main efficacy evaluation index was DCR 3 months after the end of the last treatment, and the main safety evaluation index was the proportion of CTCAE grade 3 toxicity in the entire short-term follow-up clinical trial cycle and CTCAE grade 4 & 5 toxicity reactions in the entire short-term follow-up clinical trial cycle. The collected data were analyzed and compared with the target values, and the effectiveness and safety of ProBeam360 in proton radiation therapy for patients with tumors such as intracranial, head and neck, chest, abdomen, spine, pelvis, and extremities were evaluated.

3 Overall design

3.1 Trial design

3.1.1 Trial and long-term follow-up purposes

3.1.1.1 Main purpose

To evaluate whether the main efficacy evaluation index of ProBeam360 in radiotherapy for cancer patients reached the target value 3 months after the end of the last treatment. The main safety evaluation index: whether the proportion of CTCAE grade 3 toxicity is lower than the acceptable value, and whether CTCAE grade 4 and 5 toxic reactions occur.

3.1.1.2 Secondary purposes

When evaluating the use of ProBeam in radiation therapy for tumor patients, the secondary effectiveness evaluation indicators ORR, DCR, tumor markers (if necessary), tumor-specific symptoms, and product usability evaluation are actually the actual situation.

When evaluating the use of ProBeam in radiation therapy in tumor patients, the proportion of secondary safety evaluation indicators CTCAE grade 1 and 2 toxicity, laboratory tests, ECOG physical status grade, adverse event rate, serious adverse event rate, The actual situation of the incidence of device defects.

3.1.2 Choice of trial method and justification

This trial was designed using the prospective, two-center, single-group target value method.

- (1) Prospective study: Adopt a research approach that traces from the present to the future. Prospective studies can establish cause and effect; There are unified diagnosis, detection and evaluation standards for the obtained data, so the data processing is controllable.
- (2) Single centers: Select 1 clinical trial institution to carry out the clinical trial.
- (3) Single-group target value method: Because the same device of the experimental medical device is radioactive and difficult to obtain, the existing treatment method is not feasible due to objective conditions, so the single-group target value method is adopted. Moreover, the applicable population and main evaluation indicators of experimental medical devices can be fully defined and relatively stable; The main evaluation index adopts the effective rate mentioned in the "Guidelines for the Technical Review of Clinical Evaluation of Proton Carbon Ion Therapy System" (CFDA Circular No. 4 [2018]), which is relatively objective and reproducible. According to the Guidelines for the Technical Review of Clinical Evaluation of Proton Carbon Ion Therapy Systems, the target value of therapeutic response rate for

experimental medical devices should be at least 80%, and the expected value should be 95%. Among them, the effective definition is: CR+PR+SD (complete response CR, partial response PR, disease stable SD), which is basically consistent with the definition of tumor disease control rate in this clinical trial. Therefore, no control group was set up in this clinical trial, and the single-group target value method was used to evaluate whether the tumor disease control rate reached the target value (80%) and the main safety evaluation index CTCAE 3 when ProBeam was used in radiotherapy for tumor patients. Whether the proportion of grade toxicities is less than acceptable (5%) and whether the proportion of CTCAE grade 4 and 5 toxicities is acceptable (0%).

